6.3.1 Day 1 of Clinical Trial

The following procedures will be performed at Day 1:

- Review inclusion and exclusion criteria;
- Perform targeted physical examination;
- Measure vital signs;
- Perform clinical laboratory assessments;
- Perform 12-lead ECGs at 1 hour and 6 hours post-dose;

Note: If a 12-lead ECG was not performed at Screening, the subject should have a pre-dose ECG performed in addition to the post-dose ECGs.

- Obtain blood sample for PD analyses as follows: pre-dose (within 2 hours before the first dose of study drug) and post-dose (within 1 hour);

Note: The exact time (in minutes) of the blood sample(s) must be recorded in the eCRF.

- Record concomitant medications;

- Record AEs;
- Assess NIAID score;
- Record standard of care received;
- Perform randomization; and
- Administer study drug (to hospitalized subjects only).

Note: Outpatient subjects will take the study drug at home according to their usual schedule.

6.3.2 Day 4 of Clinical Trial

The following procedures will be performed at Day 4, for subjects who are currently admitted to the hospital as inpatients:

- Perform targeted physical examination;
- Measure vital signs;
- Perform clinical laboratory assessments;
- Record concomitant medications;
- Assess NIAID score;
- Record standard of care received;
- Record AEs; and
- Administer study drug.

The following assessments will occur via telephone at Day 4, for subjects who are outpatients:

- Record concomitant medications;
- Record symptoms;
- Assess NIAID score;
- Record standard of care received; and
- Record AEs.

6.3.3 Day 7 of Clinical Trial

The following procedures will be performed at Day 7 for all subjects as indicated:

- Perform targeted physical examination;
- Measure vital signs;
- Perform clinical laboratory assessments;

Note: Subjects who are outpatients may use a local laboratory.

- Perform 12-lead ECG (inpatients only);

- Obtain blood sample for PD analyses post-dose (within 1 hour);

Note: The exact time (in minutes) of the blood sample must be recorded in the eCRF.

Note: Subjects who are outpatients may use a local laboratory.

- Record concomitant medications;
- Assess NIAID score;
- Assess subject diary compliance (for outpatient subjects only);
- Record standard of care received;
- Record AEs; and
- Administer study drug (to hospitalized subjects only).

Note: Outpatient subjects will take the study drug at home according to their usual schedule.

6.3.4 Day 10 of Clinical Trial

The following procedures will be performed at Day 10 for subjects who are currently admitted to the hospital as inpatients:

- Perform targeted physical examination;
- Measure vital signs;
- Perform clinical laboratory assessments;
- Record concomitant medications;
- Assess NIAID score;
- Record standard of care received;
- Record AEs; and
- Administer study drug.

6.3.5 Day 13 of Clinical Trial

The following procedures will be performed at Day 13 for all subjects as indicated:

- Measure weight;
- Perform targeted physical examination;
- Measure vital signs;
- Perform clinical laboratory assessments;

Note: Subjects who are outpatients may use a local laboratory.

- Obtain blood sample for PD analyses post-dose (within 1 hour);

Note: The exact time (in minutes) of the blood sample must be recorded in the eCRF.

Note: Subjects who are outpatients may use a local laboratory.

- Record concomitant medications;
- Assess NIAID score;
- Assess subject diary compliance (for outpatient subjects only);
- Record standard of care received;
- Record AEs; and
- Administer study drug (to hospitalized subjects only).

Note: Outpatient subjects will take the study drug at home according to their usual schedule.

6.3.6 Day 16 of Clinical Trial

The following procedures will be performed at Day 16 for subjects who are currently admitted to the hospital as inpatients:

- Perform targeted physical examination;
- Measure vital signs;
- Perform clinical laboratory assessments;
- Record concomitant medications;
- Assess NIAID score;
- Record standard of care received;
- Record AEs; and
- Administer study drug.

6.3.7 Day 19 of Clinical Trial

The following procedures will be performed at Day 19 for subjects who are currently admitted to the hospital as inpatients:

- Perform targeted physical examination;
- Measure vital signs;
- Perform clinical laboratory assessments;
- Record concomitant medications;
- Assess NIAID score;
- Record standard of care received;
- Record AEs; and
- Administer study drug.

6.3.8 Day 22 of Clinical Trial

The following procedures will be performed at Day 22 for all subjects as indicated:

- Perform targeted physical examination;
- Measure vital signs;
- Perform clinical laboratory assessments;
Note: Subjects who are outpatients may use a local laboratory.
- Obtain blood sample for PD analyses post-dose (within 1 hour);
Note: The exact time (in minutes) of the blood sample must be recorded in the eCRF.
Note: Subjects who are outpatients may use a local laboratory.
- Record concomitant medications;
- Assess NIAID score;
- Assess subject diary compliance (for outpatient subjects only);
- Record standard of care received;
- Record AEs; and
- Administer study drug (to hospitalized subjects only).

Note: Outpatient subjects will take the study drug at home according to their usual schedule.

6.3.9 Day 25 of Clinical Trial

The following procedures will be performed at Day 25 for subjects who are currently admitted to the hospital as inpatients:

- Perform targeted physical examination;
- Measure vital signs;
- Perform clinical laboratory assessments;
- Record concomitant medications;
- Assess NIAID score;
- Record standard of care received;
- Record AEs; and
- Administer study drug.

6.3.10 Day 28 (End of Treatment) of Clinical Trial

The following procedures will be performed at Day 28 for all subjects as indicated:

- Perform targeted physical examination;
- Measure vital signs;

- Perform clinical laboratory assessments;

Note: The exact time of the blood sample (in minutes) must be recorded in the eCRF.

Note: Subjects who are outpatients may use a local laboratory.

- Obtain blood sample for PD analyses post-dose (within 1 hour);

Note: The exact time of the blood sample (in minutes) must be recorded in the eCRF.

Note: Subjects who are outpatients may use a local laboratory.

- Record concomitant medications;

- Assess NIAID score;

- Assess subject diary compliance (for outpatient subjects only);

- Record standard of care received;

- Record AEs; and

- Administer study drug (to hospitalized subjects only).

Note: Outpatient subjects will take the study drug at home according to their usual schedule.

6.4 Follow-Up Visit (Day 35)

The following procedures will be performed at the follow-up visit (Day 35):

- Perform targeted physical examination;
- Measure vital signs;
- Record concomitant medications;
- Record standard of care received; and
- Record AEs.

All subjects will undergo a follow-up visit at Day 35. A telephone follow-up visit may be performed in lieu of the Day 35 follow-up visit if the subject is unable to attend in person. In that case, the procedures listed below in Section 6.5 will be performed.

6.5 Telephone Follow-Up (Day 60)

All subjects will undergo a telephone follow-up visit at Day 60. The purpose of the telephone follow-up is to assess survival status and evaluate for COVID-19 relapse. The following procedures will be performed during the telephone follow-up (Day 60):

- Record concomitant medications; and
- Record AEs.

6.6 Early Termination Visit and Withdrawal Procedures

The EOT for subjects completing the clinical trial is Day 28. For subjects who are withdrawn from the clinical trial prior to completion, all Day 28 procedures (see Section 6.3.10) will be performed at an early termination visit. Subjects who are withdrawn and complete an early termination visit will also undergo a telephone follow-up at Day 60.

7 ENDPOINTS

7.1 Primary Endpoint

The primary endpoint is the safety of ADX-629, determined by evaluation of the following:

- AEs;
- Safety laboratory tests (including chemistry, hematology, coagulation parameters, and urinalysis);
- Vital signs (including heart rate, blood pressure, respiratory rate, temperature, and oxygen saturation);
- Physical examinations; and
- 12-lead ECGs.

7.2 Secondary Endpoints

The key secondary endpoint is the NIAID ordinal scale score over Day 1 through Day 28.

Additional secondary endpoints include the following:

- Proportion of subjects alive and not mechanically ventilated over Day 1 through Day 28;
- Time to recovery (for hospitalized subjects at Screening), defined as the first day on which the subject satisfies 1 of the following 3 categories from the NIAID ordinal scale:
 - Hospitalized, not requiring supplemental oxygen – no longer requires ongoing medical care;
 - Not hospitalized, limitation on activities and/or requiring home oxygen; or
 - Not hospitalized, no limitations on activities;
- Time to recovery (for non-hospitalized subjects at Screening), defined as the second consecutive day on which the subject has an improvement in the NIAID ordinal scale by 1 point (e.g., NIAID scale 7 to 8);
- Proportion of subjects alive and not in the intensive care unit over Day 1 through Day 28;
- Proportion of subjects alive and not in the hospital over Day 1 through Day 28;
- Proportion of subjects alive and not on supplemental oxygen over Day 1 through Day 28;
- Mortality; and
- Time to hospital discharge (for hospitalized subjects).

7.3 Pharmacodynamic Endpoints

The PD endpoints will include the following:

- RASP plasma concentrations; and
- Plasma exploratory biomarker concentrations (e.g., IL-1 β , IL-6, IL-10, and tumor necrosis factor alpha).

8 SAFETY ASSESSMENTS

The safety of ADX-629 will be determined by evaluation of the following:

- AEs;
- Safety laboratory tests (including chemistry, hematology, coagulation parameters, and urinalysis);
- Vital signs (including heart rate, blood pressure, respiratory rate, temperature, and oxygen saturation);
- Physical examinations; and
- 12-lead ECGs.

8.1 Adverse Events

An AE is defined as any untoward medical occurrence in a clinical investigation subject administered a pharmaceutical product, which does not necessarily have a causal relationship with this treatment. An AE can therefore be any unfavorable and/or unintended sign (including an abnormal laboratory finding), symptom, or disease temporally associated with the use of an investigational medicinal product, whether or not related to the investigational medicinal product. All AEs, including observed or volunteered problems, complaints, or symptoms, are to be recorded on the appropriate eCRF.

AEs, which include clinical laboratory test variables, will be monitored and documented from the time of informed consent until the last clinical trial visit, including the telephone follow-up. Subjects should be instructed to report any AE that they experience to the Investigator, whether or not they think the event is due to clinical trial treatment. Beginning at Screening, Investigators should make an assessment for AEs at each visit and record the event on the appropriate AE eCRF.

Wherever possible, a specific disease or syndrome rather than individual associated signs and symptoms should be identified by the Investigator and recorded on the eCRF. However, if an observed or reported sign or symptom is not considered a component of a specific disease or syndrome by the Investigator, it should be recorded as a separate AE on the eCRF. Additionally, the condition that led to a medical or surgical procedure (e.g., surgery, endoscopy, tooth extraction, or transfusion) should be recorded as an AE, not the procedure itself.

Any medical condition already present at Screening should be recorded as medical history and should not be reported as an AE unless the medical condition or signs or symptoms present at baseline changes in severity, frequency, or seriousness at any time during the clinical trial. In this case, it should be reported as an AE.

Clinically significant abnormal laboratory or other examination (e.g., ECG) findings that are detected during the clinical trial or are present at Screening and significantly worsen during the clinical trial should be reported as AEs, as described below. The Investigator will exercise his or her medical and scientific judgment in deciding whether an abnormal laboratory finding or other abnormal assessment is clinically significant. Clinically significant abnormal laboratory values occurring during the clinical trial will be followed until repeat tests return to normal, stabilize, or are no longer clinically significant. Abnormal test results that are determined to be an error should not be reported as an AE. Laboratory test results that are abnormal, but not clinically significant

as determined by the Investigator, should not be reported as an AE. Laboratory abnormalities or other abnormal clinical findings (e.g., ECG abnormalities) should be reported as an AE if any of the following are applicable:

- If an intervention is required as a result of the abnormality;
- If action taken with the study drug is required as a result of the abnormality; or
- Based on the clinical judgment of the Investigator.

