Although PK variability was observed, a linear correlation was evident in C_{max} and AUC as dose increased. The half-life was consistent across cohorts and days, with mean values in multiple day exposures ranging from 3.49 hours to 6.83 hours. Little to no accumulation of ADX-629 was observed across all cohorts. At the highest dose (600 mg BID), C_{max} was 1700 ng/mL (approximately 8.5 μ M) and AUC from time 0 to 12 hours (AUC_{0-12}) was 7220 h*ng/mL. At the closest dose to the clinical dose (350 mg BID), a C_{max} of 1180 ng/mL (approximately 5.8 μ M) and an AUC_{0-12} of 4110 h*ng/mL were consistent with an adequate molar ratio to achieve stoichiometric efficacy against elevated RASP. A decrease in free MDA levels was observed in the plasma of healthy volunteers over 10 days of oral dosing with ADX-629 600 mg BID that was statistically significantly greater than that of subjects treated with placebo. Following ingestion of a high-fat meal on Day 10 of dosing with ADX-629 600 mg BID or placebo, levels of free fatty acids were statistically significantly lower, and levels of HDL were statistically significantly higher, in ADX-629-treated subjects compared with placebo-treated subjects, potentially representing additional anti-inflammatory activity of ADX-629.

The Investigator's Brochure provides more details of the clinical trials conducted with ADX-629.

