3 CLINICAL TRIAL DESCRIPTION

3.1 Summary of Clinical Trial Design

ADX-629-COVID-19-001 is a Phase 2a, randomized, double-blind, placebo-controlled, clinical trial to evaluate the safety, tolerability, efficacy, and PD of ADX-629, administered orally, in adult subjects with COVID-19 of moderate severity prior to the requirement for mechanical ventilation. Approximately 30 subjects will be randomized in a 2:1 ratio (ADX-629 to placebo) to receive either ADX-629 300 mg BID or placebo BID for up to 28 days.

The reason for hospital admission (for hospitalized subjects), the standard of care (see Section 5.6.3) followed for each subject and site, and whether any care decisions were based on resource limitations will be clearly documented for all subjects.

Treatment will begin on Day 1 following randomization. In addition to ADX-629 or placebo, all subjects will receive standard of care treatment for COVID-19. Treatment may commence whether a subject is hospitalized or is treated as an outpatient at Screening. During the Treatment Period (Days 1 to 28/End of Treatment [EOT]), all subjects will receive study drug (either ADX-629 or placebo) BID. The study drug will continue to be taken on an outpatient basis if a subject is discharged from the hospital prior to Day 28 for hospitalized subjects. If a subject is placed on mechanical ventilation and/or is otherwise unable to ingest an oral tablet, dosing will be stopped. However, the subject will continue to be monitored for efficacy and safety. Dosing of the study drug may resume once the subject is able to safely ingest an oral tablet.

All subjects will also have an assessment using the NIAID ordinal scale score (see Appendix C) daily on Days 1 to 28/EOT. The NIAID score will be evaluated directly for inpatient subjects and assessed via a subject diary for outpatient subjects through Day 28.

After treatment is completed, subjects will undergo a follow-up visit on Day 35 (± 3 days) and a telephone follow-up on Day 60 (± 3 days). The purpose of the telephone follow-up is to assess survival status and evaluate for COVID-19 relapse. A telephone follow-up visit may be performed in lieu of the Day 35 follow-up visit if the subject is unable to attend in person.

The clinical trial will be conducted at approximately 3 sites in the United States.

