5 CLINICAL TRIAL TREATMENTS

5.1 Treatment Groups

All subjects will receive either ADX-629 300 mg BID or placebo BID for up to 28 days. The study drug will be administered orally as a tablet, at the discretion of the Investigator.

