9.2.2 Analysis of Safety

AEs will be classified according to the Medical Dictionary for Regulatory Activities (MedDRA) and will be presented by counting the number of subjects reporting each event by treatment. The number (percentage) of subjects reporting TEAEs and SAEs for each preferred term will be tabulated by system organ class (SOC), by SOC and severity, and by SOC and relationship to the study drug. If more than 1 event occurs with the same preferred term for the same subject, the subject will be counted only once for that preferred term using the most severe or related occurrence for the summary by severity or relationship to study drug, respectively.

If specific AEs occur in a sufficient number of subjects, an exposure-response model may be developed as a secondary analysis.

Clinical laboratory values (excluding efficacy laboratory parameters) will be summarized by treatment arm, including changes from baseline at each visit.

Vital signs and change from baseline in vital signs will be summarized descriptively at each visit by treatment arm.

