#### *3.6.1 Adverse Events (AEs)*

AEs will be captured from the date of informed consent through study completion. All AEs will be coded to system organ class and preferred term using MedDRA version 23.1.

Treatment-emergent adverse events (TEAEs) are defined as AEs that start after the first dose of study drug. AEs with partially missing onset dates will also be included as treatment emergent when the month (if it exists) and the year occur on or later than the month and year of the first dose date.

An overview of AEs will be provided including counts and percentages of subjects (and event counts) with the following:

- Any TEAEs (overall and by maximum severity)

- Any study drug related TEAEs
- Any serious AEs (SAEs)
- Any treatment-emergent serious AEs (TESEAEs)
- Any TEAEs leading to discontinuation of study drug
- Any AEs leading to death

Counts and percentages of subjects (and event counts) will also be presented by system organ class and preferred term for each of the categories in the overview.

Listings will be presented for all AEs and hospitalization data.

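### SAP 3.6.1 gives the TEAE window a start but no end, so by-arm TEAE counts pool events during dosing with events up to the Day 60 call, and no planned table separates them

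*Protocol*

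**What the plan says.** Collection runs long. Protocol 8.1 states that adverse events "will be monitored and documented from the time of informed consent until the last clinical trial visit, including the telephone follow-up", and SAP 3.6.1 agrees: "AEs will be captured from the date of informed consent through study completion". Protocol 6.5 lists AE recording among the procedures of the Day 60 call, which has a window of 3 days either side (Protocol 3.1).

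Dosing is short. Protocol 5.1: "All subjects will receive either ADX-629 300 mg BID or placebo BID for up to 28 days". Under Protocol 4.3, subjects who stop study drug early are still followed to Day 60 unless they withdraw consent for follow-up.

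The definition that joins the two is in SAP 3.6.1: "Treatment-emergent adverse events (TEAEs) are defined as AEs that start after the first dose of study drug". It has no limit relative to last dose. The tables are counts and percentages of subjects; in Protocol 9.2.2, "The number (percentage) of subjects reporting TEAEs and SAEs for each preferred term will be tabulated" by system organ class, severity and relationship to study drug. SAP 3.6.1 adds overview rows for drug-related TEAEs and for TEAEs leading to discontinuation, and a listing of all AEs. Neither document plans a split by time of onset or an exposure-adjusted rate. Protocol 8.3 mentions a 30-day window for SAE reporting, but does not say what it runs from and does not limit the TEAE definition.

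**The concern.** Safety is the primary endpoint, and adverse events are its first listed component (Protocol 7.1). With about 30 subjects randomized 2:1, the arms hold about 20 and 10, so one placebo subject is worth 10 percentage points. A subject whose only event starts on Day 50 counts in the same row as one whose event starts on Day 2.

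The plan's own pharmacokinetic figures suggest that drug is gone soon after dosing stops: Protocol 1.1.2 gives the half-life "with mean values in multiple day exposures ranging from 3.49 hours to 6.83 hours". If the drug effect ends with exposure, background events after washout raise the percentages in both arms and narrow the gap between them. An on-drug excess would then be harder to see in the tables meant to show it.

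**Working it through.** The documents give no AE rate and no target difference for safety, so there is no planned figure to reproduce. The rates below are assumptions.

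**Share of the window after last dose** = (last contact day − last dose day) / last contact day.

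- Completer, Day 60: (60 − 28)/60 = 32/60 = 53.3%.
- Across the visit window: Day 57, 29/57 = 50.9%; Day 63, 35/63 = 55.6%.
- Dosing stopped on Day 14: 46/60 = 76.7%. On Day 7: 53/60 = 88.3%.
- Washout: 5 × 6.83 h = 34.15 h = 1.42 days. Counting this as on drug, the completer's share is (32 − 1.42)/60 = 51.0% at Day 60 and (29 − 1.42)/57 = 48.4% at Day 57.

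These are shares of calendar time, not of events.

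**Effect on the risk difference.** Let *b* be the background rate during Days 1–28, HR the on-drug hazard ratio, and *c* the rate in both arms after Day 28. For a completer with cut-off at Day T:

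RD(T) = [exp(−28b) − exp(−28b·HR)] × exp(−c(T − 28))

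so RD(60)/RD(35) = exp(−25c), whatever the HR.

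Take b = 0.02/day and HR = 3. The bracket is exp(−0.56) − exp(−1.68) = 0.571 − 0.186 = 0.385.

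| Off-drug rate c | RD to Day 35 | RD to Day 60 | Loss, 1 − exp(−25c) |
|---|---|---|---|
| 0.02 (unchanged) | 0.385 × exp(−0.14) = 33.5 points | 0.385 × exp(−0.64) = 20.3 points | 39% |
| 0.005 (a quarter) | 0.385 × exp(−0.035) = 37.2 points | 0.385 × exp(−0.16) = 32.8 points | 12% |
| 0.002 (a tenth) | 0.385 × exp(−0.014) = 37.9 points | 0.385 × exp(−0.064) = 36.1 points | 5% |

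With the rate unchanged off drug, b = 0.01 gives 1 − exp(−0.25) = 22% and b = 0.03 gives 1 − exp(−0.75) = 53%.

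**Individual preferred terms.** At 0.001/day the loss is 1 − exp(−0.025) = 2.5%; at 0.002/day it is 1 − exp(−0.05) = 4.9%, even with the rate unchanged off drug.

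**Ratio scale.** Here the pull toward 1 does not vanish at lower risks. With on-drug risks of 10% and 20% (ratio 2) and an unchanged background, the off-drug risk is q = 1 − 0.9^(32/28) = 0.113. The Day 60 risks are 1 − 0.9 × 0.887 = 20.2% and 1 − 0.8 × 0.887 = 29.0%, a ratio of 1.44. At a quarter or a tenth of the rate the ratio is 1.77 or 1.89. With about 10 placebo subjects, ratios for uncommon terms are hardly readable in any case.

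**The case against.** The strongest case on the other side has five parts.

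- **Late events may be few.** Inpatients have AE contacts on ten days from Day 1 to Day 28 and outpatients on six; after that only Days 35 and 60 remain, the last by telephone. Conditions present at Screening are not AEs unless they change (Protocol 8.1), so lingering symptoms do not automatically become late TEAEs. This stands. A constant rate over 60 days is the upper end of what is plausible, and the lower rows of the table matter as much as the first.
- **Related TEAEs are summarized separately.** Timing from dosing enters the causality judgment, so clearly late events should mostly drop out there. This helps in part. Protocol 8.1.3 reserves a yes for events with no other identifiable cause, and in ill patients on standard of care another cause is often at hand. The all-cause comparison by arm does not depend on that judgment, and it is the one that is pooled.
- **All AEs are listed.** True, but a listing leaves the cut-off to be chosen after unblinding.
- **A long window catches delayed harm.** This stands. Plasma half-life shows when drug leaves, not when harm stops appearing, and the highest Phase 1 dose was given for only 10 days (Protocol 5.2). It is a reason to keep the Day 60 table, not to have only that table.
- **The trial is exploratory and no AE test is planned.** This stands, and it makes power the wrong measure. The point concerns how descriptive tables read.

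A reader might also infer that collecting AEs to Day 60 is itself a fault. It is not: the gap lies only in the missing end date in SAP 3.6.1.

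**Conclusion.** The gap is real and modest. The SAP pools on-drug and post-drug onsets in its all-cause TEAE tables, and about 53% of a completer's window (51% to 56% across the visit window) follows the last dose.

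Whether this hides anything is conditional. If the drug effect ends soon after dosing, extending the cut-off from Day 35 to Day 60 at an assumed 0.02/day reduces the risk difference for an any-TEAE outcome by about 39%, 12% or 5%, according to how far the background rate falls off drug. For uncommon preferred terms the difference barely moves. If harm is delayed, the longer window catches it.

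Two stronger readings are tempting and unsupported. One is that over half of the TEAEs will be off drug: the 53% is time, and the documents give no event rates. The other is that a true drug effect will be diluted as a matter of course: that needs both a prompt end of effect and an appreciable late background. No on-drug event is lost from the tables under any reading. Laboratory tests are scheduled to Day 28 and ECGs to Day 7, so the point is confined to the AE tables.

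SAP Section 7 defers programming detail to a separate document. A split might appear there, but the SAP does not commit to one. This is a cheap improvement to the primary safety readout.

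**What to change.** Leave AE collection unchanged. Before unblinding, add to SAP 3.6.1:

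1. An on-treatment TEAE overview and SOC/PT table by arm, covering onsets from first dose through last dose plus a stated allowance. Seven days is one choice: it matches the Day 35 visit for completers (28 + 7 = 35). It exceeds the 34-hour washout and leaves 7/35 = 20% of that window after last dose, so the SAP should give its reason for whichever allowance it adopts.
2. A separate table of onsets after that cut-off, up to Day 60.
3. A rule for partial onset dates in the split. The present rule settles only whether an event is treatment-emergent, not which side of the cut-off it falls on.

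Keep the existing table of all onsets to Day 60, and keep reporting SAEs and deaths over the whole period.

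The cost is SAP wording and one extra set of tables from dates already collected, with no new visits or data. The downside is that the on-treatment table omits delayed events; the retained Day 60 table still shows them.
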